Individuals will attend a total of 5 visits over the course of the 5 month study (**Figure 3**). Twenty (20) individuals will be randomized to treatment for 4 months. At the initial screening visit, participants will complete a short questionnaire about their medical history, medication history, have safety labs assessed and will have their blood pressure measured. Also, individuals will be given information on a self-paced, standardized wellness program including exercise material and a nutrition guide, called the Dietary Approaches to Stop Hypertension (DASH) [87] to be completed over the next 4 weeks +/- 5 days to adjust for the participant's schedule. The DASH is recommended in national hypertension guidelines [87] and information regarding exercise and fitness is based on guidelines from the National Institute on Aging. The purpose of the wellness program is to educate participants on ways to improve their health, specifically BP, in ways that do not involve medication. After the 4 week (+/- 5 days) wellness program, BP will be taken to assess the success of the wellness program. Participants should be seated 5 minutes

with their legs uncrossed before BP measures are taken. A total of 3 readings will be taken. The average of these 3 readings will designate the mean, which will be used to assess study inclusion.

Participants whose BP average remains in the targeted range (mean systolic 130 – 160 mmHg, and mean diastolic 70 - 100 mmHg) will be randomized to one of the two treatment arms (ramipril vs. placebo). Individuals whose BP is lowered as a result of the wellness program will not be included in the study (i.e. randomized).

For subjects who are randomized, this visit will serve as their Baseline visit. The 20 subjects will be randomized in a 1:1 ratio by the UW Pharmaceutical Research Center (PRC) to receive an initial ramipril dose of 5mg to be taken once daily (N=10) vs. matching placebo (N=10).

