At baseline and the 4 month follow-up visit, participants will have fasting CSF collected, complete tests of vascular reactivity (**See Vascular Endpoints below**), provide an update on medical problems and medications, review any potential side effects and complete a 1 hour cognitive battery. A fasting blood draw will occur at the baseline visit to assess lipid profile, a potential factor in CSF a-beta levels. While cognitive task performance is not a primary outcome variable, we include this measure because cognition has been linked to BP and antihypertensive medication.

There will be 2 safety visits between the Baseline and Month 4 visits. The safety visits will be at 1) week 1-2 and 2) week 3-4 after the Baseline visit. During the 2 safety visits, participants will have safety labs (creatinine, potassium and urine pregnancy), have blood pressure taken, report any changes in medications or health as well as review and report potential side effects.

The primary endpoint of the proposed study is to determine the effect of ramipril therapy on CSF Aβ levels in a group at risk for developing AD. The secondary endpoints are the effect of centrally acting ramipril therapy on CSF ACE levels, biomarkers of peripheral vascular reactivity as measured by brachial artery flow-mediated vasodilation (FMD) and aortic augmentation index (AAIx) and cognitive task performance. Randomization will be stratified based on sex and APOE genotype, a risk factor for AD. Subjects and investigators will be blinded to the identity of the medication and BP readings obtained throughout the study. [name] will call in ApoE results to the PRC for randomization in order to maintain blinding. Compliance will be assessed by pill count at each of the follow-up visits. The study coordinator will review the possible side effects related to ramipril at each visit, including mild cough, hyperkalemia and changes in kidney function.

All outcomes outlined in the initial protocol, including ApoE testing, have been completed. However, the PI and her collaborators will continue to store all samples and tissue at the UW Madison for future testing.

D. 2. Summary of the Experimental Procedures

D. 2. 1. CSF Collection

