Blood, urine and CSF samples will be collected after a 12-hour overnight fast at baseline and month 4 visits. Lipid profile from a fasting blood draw will be done at the baseline visit only. Potassium and creatinine levels will be measured from non-fasting blood draws done at screening and safety visits using enzymatic precipitation techniques on a Hitachi 747 analyzer with standard reagents. These studies will be performed in the UW Hospital Laboratory. Samples will be stored indefinitely and may be used for ongoing Alzheimer’s Disease related research. IRB approval will be obtained for any future use of data or samples not explicitly described in this protocol.

D. 2. 4. Cognitive Testing

Following blood and CSF collection, all subjects will be served a light breakfast. At the Baseline and Month 4 visits, cognitive tests will be administered by a trained technician according to protocols established for each test. The cognitive battery is expected to take 1½ -2 hours to

complete. To reduce practice effects, alternate forms of the above tests have been identified and validated to assure comparability. To control for variations in instrumentation, technicians will be trained to use standardized instructions for each test administered and the same technician will test a particular subject at each visit. In addition, change-scores will be determined for cognitive data obtained at baseline and month 4 visits. The change-scores of the ramipril group will be compared to the change scores of the placebo group. In this way, we will control for practice effects, and maximize internal validity (95). Details of each cognitive test are included in this application.

D. 3. Descriptions of Rationales for Each Specific Aim

D. 3. 1. Specific Aim 1: Effects of Ramipril on CSF A β 40 and A β 42

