Clinical outcome parameters will be described by means and standard deviations at each measurement time point. Regression models will be used to evaluate predictors of change in CSF variables and endothelial outcomes. Changes in clinical outcome parameters (baseline, month 4) will be analyzed using repeated-measures analysis of variance (ANOVA) to assess the effects of ramipril vs. placebo, using covariates as applicable (ANCOVA). All tests will be two-tailed tests using a significance level of 0.05.

All data for the SEAIRA trial has now been collected at the UW Madison. Data collected as a part of this study will be shared with [name], the prior PI of the SEAIRA study, now Assistant Professor at Emory University. While at Emory University, [name] plans to continue analyses on data collected during her time at the University of Wisconsin. We propose that this study now become a two-site study with [name] mentor and Co-I, [name] as the site PI for the University of Wisconsin. All physical data, data specimens including stored CSF and blood will remain at the UW. The study should however remain open so [name] may continue data analyses for this study. [name] will conduct the analyses at Emory with coded data. The UW ADRC research team will be the only institution with access to this code.

While SEAIRA is now complete, additional analyses on data from this trial need to be conducted. To accomplish this goal, data must be transferred to Emory University from the UW. Data will be sent electronically via email from the ADRC research team at UW Madison to [name] at Emory University. The transfer will be overseen by new UW PI of the project – [name]. All transmitted data will be coded. The code used to label data will be separate from the previously used SEAIRA trial ID number, so that [name] will not know or have access to the key linking identities with the data. Data to be transferred consists of neuropsychological testing data, ApoE4 genotype, abeta and ACE levels and activity in CSF, family history status, race, gender, age, self-reported income category, handedness, education level, drug randomization assignment, symptom reports during the trial, lab data including HDL, LDL, cholesterol levels, potassium, creatine, CSF cell count, smoking history, exercise history, medication and medical history information and data confirming study medication compliance.

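### For the cognitive tests, adjustment for each test's own baseline score is permitted but not specified; naming it as the covariate would probably gain precision at almost no cost

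*Combined protocol and SAP*

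**What the plan says.** Cognitive task performance is a secondary endpoint. D.1.3 explains its inclusion: "While cognitive task performance is not a primary outcome variable, we include this measure because cognition has been linked to BP and antihypertensive medication". D.2.4 provides the baseline value for every test: "At the Baseline and Month 4 visits, cognitive tests will be administered by a trained technician according to protocols established for each test". It then gives the only analysis rule specific to cognition: "The change-scores of the ramipril group will be compared to the change scores of the placebo group". The stated purpose is "In this way, we will control for practice effects, and maximize internal validity".

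D.4 lists CSF Aβ, ACE and endothelial measures as the study objective and does not mention cognition. It says that changes in clinical outcome parameters, a term it does not define, "will be analyzed using repeated-measures analysis of variance (ANOVA) to assess the effects of ramipril vs. placebo". Covariates may be added where applicable, in an ANCOVA, but none is named. Tests are two-sided at 0.05.

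On allocation, D.1.3 says "The 20 subjects will be randomized in a 1:1 ratio", that is, 10 per arm, and "Randomization will be stratified based on sex and APOE genotype, a risk factor for AD". Baseline cognition is not a stratification factor.

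**The concern.** A change score is negatively correlated with its own baseline whenever the baseline to month-4 correlation is below 1 and the two variances are similar. An arm that happens to start lower therefore tends to show the larger gain, whatever the drug does. With 10 per arm, and stratification on sex and APOE only, a sizeable chance difference in baseline test scores is quite possible. Adjusting for the baseline score removes this component and usually narrows the confidence interval.

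The score is already collected. What is missing is a statement that it will be used. As D.4 stands, one analyst could adjust for it and another could omit it, and both would be within the plan. What is at stake is the precision and reproducibility of a secondary result in a pilot whose data, under A.1, are meant to support a later grant application.

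**Working it through.** **Inputs.** 10 per arm (D.1.3); baseline and month-4 scores on every test (D.2.4); two-sided 0.05 (D.4). The documents give no SD, effect size, power or correlation for any cognitive test, so there is no stated figure to reproduce. The power statement in D.4 covers CSF Aβ and the endothelial variables only. Assumptions: equal variances at the two visits, a common baseline to month-4 correlation rho, bivariate normal scores, no dropout.

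**Step 1: does D.4's default model differ from D.2.4?** No. With two time points, the arm-by-time F of a repeated-measures ANOVA equals the squared t of the change-score comparison. On one simulated data set of 20, both came to 0.0027227.

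**Step 2: size of chance imbalance.** The difference D in baseline means has SD sqrt(2/10) = 0.447 baseline SDs. The probability that |D| exceeds 0.5 SD is about 26%.

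**Step 3: carry-over.** Given D, the expected month-4 difference is the true effect plus rho × D. Subtracting D leaves the true effect minus (1 - rho)D. At rho 0.5 and D = 0.45, the shift is 0.5 × 0.45 = 0.22 SD in size. Simulated slopes on D were -0.70, -0.50, -0.30 and -0.10 at rho 0.3, 0.5, 0.7 and 0.9; with ANCOVA they were about 0. D averages zero over randomisations, so the unconditional bias is zero. Simulated type I error was about 5% for both methods.

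**Step 4: precision.** In units of (2/10) × baseline variance:

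- change score: 2(1 - rho)
- ANCOVA: (1 - rho²) × 17/16, where 17/16 = (N - 3)/(N - 4) at N = 20 is the cost of estimating the slope
- ratio, ANCOVA to change score: (1 + rho)/2 × 17/16

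The ratio reaches 1 at rho = 2 × 16/17 - 1 = 0.88.

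**Step 5: power.** Simulated for 10 per arm, with t tests on 18 df (change score) and 17 df (ANCOVA). Two effects were tried: 1.325 SDs of change, at which the change-score test has 80% power, and 0.5 SDs of change, at which it has 19%.

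| rho (assumed) | Shift per SD of D | Variance ratio | ANCOVA power, change score 80% | ANCOVA power, change score 19% |
|---|---|---|---|---|
| 0.3 | -0.70 | 0.65 × 17/16 = 0.69 | 92% | 25% |
| 0.5 | -0.50 | 0.75 × 17/16 = 0.80 | 88% | 22% |
| 0.7 | -0.30 | 0.85 × 17/16 = 0.90 | 84% | 20% |
| 0.8 | -0.20 | 0.90 × 17/16 = 0.96 | 81% | 19%, a gain of at most about 1 point |
| 0.9 | -0.10 | 0.95 × 17/16 = 1.01 | 79% | no gain |

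At an effect of 0.3 SDs of change and rho 0.5, power is 10% against 11%.

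**The case against.** **The plan already allows the adjustment.** D.2.4 says only that change scores will be compared. It names no test and does not rule out covariates, and D.4 permits them. A reader might infer that D.2.4 fixes an unadjusted analysis; the text does not go that far. This stands, and it limits the criticism to something permitted but not specified. It does not remove it, because D.4 neither clearly covers cognition nor names a covariate.

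**The change-score comparison is valid.** A reader might infer from the carry-over that the cognitive result is systematically biased. It is not. The shift exists only given a realised imbalance and averages to zero, and type I error stays at 5%. This stands in full.

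**The practice-effect sentence is correct.** A reader might infer that the rationale in D.2.4 is mistaken. Read in place, it refers to comparing the ramipril change with the placebo change, and that comparison does remove average practice effects. D.2.4 also uses validated alternate forms. The sentence simply does not address baseline imbalance.

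**The gain rests on assumptions.** No rho is given, and an 8-point gain needs both rho near 0.5 and a very large effect. The named measure in D.3.4 is the MMSE, and Table 1 excludes scores below 27, so entry scores lie between 27 and 30. That restriction may lower rho, which would favour adjustment, but normal-theory power figures are not established for so short a scale. This stands as a limit on the size claimed.

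**Stakes and timing.** Cognition is secondary and carries no power claim, and A.1 leaves cognitive performance to a later, larger study. Data collection is complete, and section C reports publication in 2012. Both facts stand: the point is small, and a change made now cannot be called prespecified.

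**Conclusion.** The point holds as a minor, nearly free improvement. Neither D.2.4 nor D.4 names the test's own baseline score as a covariate for the cognitive comparison, and the default in both sections is the change-score test. Under the assumptions above, adjustment cuts the variance of the arm contrast by about 31% at rho 0.3, 20% at 0.5, 10% at 0.7 and 4% at 0.8. At 0.9 it is about 1% worse. For an effect of 0.5 SDs of change, the power gain is about 6 points at rho 0.3, falling to 1 point or less at 0.8. It exceeds a few points only when the effect is large or rho is low. The existence of the gap is certain from the text; its size is not, because rho is not given. Nothing here invalidates the planned test or affects the primary CSF endpoint.

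**What to change.** In D.2.4, add that for each cognitive test the month-4 score is regressed on arm and that test's baseline score, and that the adjusted arm difference with its 95% CI is the reported effect. Using the change as the outcome with the same covariate gives the identical arm estimate, so the change-score presentation can stay. Keep mean change by arm as description, and keep the statement that comparison with placebo handles average practice effects. In D.4, name cognition among the outcomes covered and the baseline score as the covariate, so that the two sections agree.

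D.4 states that all data are collected, that further analyses are to follow, and that the data to be transferred include neuropsychological results and treatment assignment. The adjusted analysis must therefore be labelled as specified after data collection and shown beside the planned change-score comparison.

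The cost is a sentence or two of text and no new data. The statistical price is one degree of freedom, which loses under 1 point of power if rho is about 0.9.

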Our overarching hypothesis is that mildly hypertensive, middle-aged, non-demented, adult children of persons with AD will exhibit lower CSF A β and ACE levels and improved endothelial function following 4 months of ramipril therapy. These vascular effects have been tied to cognition. Later work will examine whether ramipril may reduce the risk of AD in later life.

The proposed trial has the potential to draw attention to an extremely promising avenue in AD prevention. Specifically, a therapeutic intervention that reduces A β levels may delay the onset of AD pathology, or possibly one day serve as a treatment strategy. Pilot data collected from the current investigation will be used to support a NIH Pathway to Independence grant application (K99/R00), which will investigate the effects of centrally acting ACE inhibitors on biomarkers for AD (CSF and MRI perfusion), in middle-aged persons at risk for AD. Of note, the K99/R00 proposal will not only have the power and the length of follow-up needed to address the variables included in the current proposal, but it will also be designed to examine cognitive task performance. Importantly, the NIA has stated that funding pharmacologic research in order to understand the pathobiology of AD is of the highest priority. The current project serves to provide preliminary data, as well as to address initial questions surrounding the relationship

between AD and vascular factors before a larger, more expensive and more targeted research project is warranted.

A.2. Hypothesis:

We hypothesize that mildly hypertensive, middle-aged, non-demented, adult children of persons with AD will exhibit lower CSF A β and ACE levels and improved endothelial function following 4 months of ramipril therapy. These vascular effects have been tied to cognition. Later work will examine whether ramipril may reduce the risk of AD in later life.

A.3. Specific Aims:

The present study is guided by the following specific aims:

Specific Aim 1: To determine the effects of 4 months of ramipril therapy on CSF A β levels in mildly hypertensive, non-demented adult children of persons with AD when compared to subjects taking placebo.

Specific Aim 2: To evaluate the effects of 4 months of ramipril therapy vs. placebo on CSF ACE levels in mildly hypertensive, non-demented adult children of persons with AD when compared to subjects taking placebo.

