Unfortunately, the *plasma* levels of A β 40 and A β 42 are unreliable due to low A β plasma concentrations, binding of A β to carrier proteins, and cross-reactivity between A β with several plasma proteins [95-101]. Some investigators have shown that plasma levels of A β 42 are similar between AD patients and controls [101]. Others have noted an increase in plasma A β 42 concentrations in 10 to 20% of sporadic AD patients [102, 103]. Because of the inaccuracy of plasma measures at this time, the proposed protocol will measure CSF A β levels. Since these CSF biomarkers have been shown to be stable when stored at -70°C for up to 15 years, extra tubes of CSF will be collected in those participants who agree to future testing of samples [8].

D. 3. 2. Specific Aim 2: Rationale for Evaluation of Ramipril on CSF Markers of Angiotensin Converting Enzyme (ACE)

Overall, there is evidence that certain components of the renin-angiotensin system (RAS), the system that regulates ACE levels, may have a crucial role in learning and memory processes. Research has shown that there is a relationship between CSF ACE levels and AD. For instance, ACE gene variants are linked to AD risk in several populations. Specifically, studies have reported elevated levels of angiotensin-converting enzyme (ACE) in the hippocampus, parahippocampal gyrus, frontal cortex, and caudate nucleus of AD patients. The increased ACE activity may be directly responsible for cognitive impairment in AD because the enhanced formation of angiotensin II would result in an increased inhibitory effect of angiotensin II on acetylcholine release. Furthermore, Levels of CSF ACE reduced in Alzheimer's disease, Parkinson's disease, and supranuclear palsy [104].

D. 3. 3. Specific Aim 3: Rationale for Evaluation of Ramipril on Vascular Function

One objective of this trial is to examine the effects of the ACE-I, ramipril peripheral endothelial function as measured by brachial artery flow-mediated vasodilation (FMD) and aortic augmentation index (AAIx). The effect of ACE inhibitors on large and small artery endothelial function has been assessed in clinical trials in patients with essential hypertension. It is well established that ACE-I reduce blood pressure and improve FMD. For instance, one study reported that FMD corrected for resting diameter (FMDcorr) was lower in patients taking ACE-I ($3.0 \pm 0.2\%$) compared with participants treated with beta-blockers ($4.2 \pm 0.3\%$, $p < 0.01$) [105].

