D. 3. 4. Rationale for Cognitive Testing A three-year study of 3,217 elderly residents of Cache County, Utah, initially found that the use of some antihypertensive medications at baseline was associated with lower incidence of AD. More recently, ACE-I have been shown to influence cognitive task performance in clinical trials specifically targeting AD related memory problems. Of note, the current proposed study will incorporate the same cognitive outcome measure (the MMSE) that has been shown to be sensitive to ACE-I treatment. Two clinical trials, Syst-Eur and PROGRESS both reported improved cognitive test scores in participants with mild to moderate AD (controlled for vascular dementia) as a result of treatment with ACE-I.

Furthermore, Sink et al. examined the influence of ACE-I that do and do not cross the blood brain barrier (BBB). The authors concluded that BBB crossing ACE-I participants in the BBB crossing group had a significantly lower incidence of developing AD as well as significantly reduced MMSE decline in AD patients compared to CCB and ACE inhibitors. This factor is of particular relevance because the ACE-I in the current proposal, ramipril, is an ACE-I that crosses the BBB. These results were presented at the AGS 2007 Annual Scientific Meeting: Abstract P36. Presented May 5, 2007.

D. 4. Data Analysis and Statistical Considerations The study objective is to evaluate the effects of 4 months of ramipril therapy vs. placebo on mean changes in CSF A β , ACE and mean changes in measures of peripheral endothelial function. While we are not aware of any research examining the effect of ACE-Is on CSF A β , cognitive improvements due to ramipril have been reported in as few as 5 days [29]. In reference to reductions in plasma ACE, ramipril is one of the most potent ACE-Is available and has a trough-to-peak ratio around 50% [106, 107]. When ACE-Is are injected intracerebroventricularly, A β reduction can occur in as few as 2 hours. A sample size of 10 subjects per arm should have greater than 80% power to detect an 8% change in CSF A β , the primary outcome, and greater than 90% power to detect significant

change in endothelial variables. Based on the sample size estimates, 20 subjects will be recruited for the 4-month clinical trial.

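### Do the power claims for 10 per arm contradict the protocol's own description of the trial as preliminary, and its own FMD example?

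*Combined protocol and SAP*

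**What the plan says.** D.4 sets the sample size: "A sample size of 10 subjects per arm should have greater than 80% power to detect an 8% change in CSF" Aβ. This is the main endpoint; for endothelial variables D.4 claims power above 90%, without naming an effect. The 20 participants follow from these estimates. D.4 gives no SD, no baseline-to-month-4 correlation, no source for the 8% and no endothelial effect size. It also says "we are not aware of any research examining the effect of ACE-Is on CSF" Aβ. Tests are two-sided at 0.05. The analysis is repeated-measures ANOVA, or ANCOVA, of ramipril against placebo.

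A.1 says of a later grant project that it "will not only have the power and the length of follow-up needed to address the variables included in the current proposal", and that it will also examine cognitive performance. Of this trial it says: "The current project serves to provide preliminary data".

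A.2 hypothesises lower CSF Aβ "and ACE levels and improved endothelial function following 4 months of ramipril therapy", without naming placebo. The three aims in A.3 do name it.

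D.3.3, the rationale for the vascular endpoints, states: "It is well established that ACE-I reduce blood pressure and improve FMD". The illustration that it then offers points the other way: "For instance, one study reported that FMD corrected for resting diameter (FMDcorr) was lower in patients taking ACE-I". The means were 3.0 ± 0.2% in that group and 4.2 ± 0.3% in the comparison group, who took beta-blockers; the reported p value is below 0.01.

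**The concern.** Three things look wrong together. First, D.4 treats 20 participants as enough for these outcomes, while A.1 seems to leave adequate power for the same outcomes to another study. A reader could ask whether this is a powered test or an estimation pilot. Second, the 90% claim names no effect, and the one numeric endothelial effect in the document has FMD lower on the ACE inhibitor, against a comparator this trial does not have. Third, an 8% change could mean a change within the ramipril arm or a difference from placebo, and the two need different SDs.

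The stake is interpretation. The 2014 update in Section C reports publication, a career award and four pending applications that build on the trial, and D.4 foresees more analyses at two sites. If the power statement were taken at face value, a non-significant Aβ result might be read as showing no effect. If A.2 were taken alone, a within-arm change might be presented as the treatment effect.

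**Working it through.** **Inputs.** From the document: 10 per arm, 8% change, power above 80% and above 90%, two-sided 0.05 (D.1.3, D.4); FMD means 3.0 and 4.2 with ± 0.2 and ± 0.3 (D.3.3). Not given, so assumed below: every SD, every correlation, whether ± means SD or SE, and the group sizes behind the FMD example.

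**The plan's figures.** Neither can be reproduced, because D.4 gives no SD and no endothelial effect. The formula can only be solved backwards for what the stated power requires.

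**CSF Aβ, between arms.** Two-sample t test, df = 18, noncentrality d × √(10/2). Power of 80% needs d = 1.325.

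- SD limit: 8 / 1.325 = 6.04% (SD of percent change).
- Baseline-adjusted (df = 17, equal variances): the limit on the SD of change is 6.3% at correlation 0.8 and 6.9% at 0.5.

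| Assumed SD of percent change | Unadjusted power |
|---|---|
| 5% | 0.92 |
| 6% | 0.80 |
| 8% | 0.56 |
| 10% | 0.40 |
| 15% | 0.20 |

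The claim holds at the top of this table and fails below it. Nothing in the document says which row applies.

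**CSF Aβ, within the ramipril arm.** A paired t test with n = 10 needs d = 0.996, so the limit is 8 / 0.996 = 8.03%. At that SD the between-arm test has power 0.56. The two readings therefore differ materially, but only one is planned. The aims compare with placebo, D.4 opens with ramipril against placebo on mean changes, its ANOVA assesses ramipril against placebo, and D.2.4 compares change scores between groups for cognition. No within-arm test is specified.

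**FMD, ignoring the sign.** Difference 4.2 − 3.0 = 1.2 points. Power of 90% needs d = 1.534, so the SD limit is 1.2 / 1.534 = 0.78 points.

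- If ± is an SD: pooled SD = √((0.2² + 0.3²)/2) = 0.255, and power exceeds 0.99.
- If ± is an SE with m per group: between-patient SD = 0.255 × √m. The trial analyses change from baseline, so this must be converted: SD of change = SD × √(2(1 − r)).

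| m per group (assumed) | Between-patient SD | Change-score power, r = 0.5 | Change-score power, r = 0.8 | Baseline-adjusted power, r = 0.8 |
|---|---|---|---|---|
| 10 | 0.81 | 0.88 | 0.999 | 0.999 |
| 20 | 1.14 | 0.60 | 0.94 | 0.96 |
| 30 | 1.40 | 0.44 | 0.82 | 0.86 |

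At r = 0.5 the factor √(2(1 − r)) is 1, so that column equals the power obtained by using the between-patient SD directly. At r = 0.8 the factor is 0.632 and power is above 90% even with 20 per group. The example neither supports nor refutes the claim.

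**A.1 beside D.4.** A.1 says what the later project will have: power and length of follow-up, with cognition added. It makes no statement about power here. A pilot can be sized for an 8% change at 4 months while a larger, longer study takes the same variables further.

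**The case for a change.** The strongest case for acting is that A.1's phrase makes little sense if 20 participants already give more than 80% and 90% power, that the Aβ claim needs an SD of about 6% when D.4 knows of no prior research on the effect, and that correcting text costs nothing while analyses continue. With all 20 analysed, the 95% CI half-width is 2.101 × √(2/10) = 0.940 SD, so a zero estimate would exclude 8% only if the SD were below 8 / 0.940 = 8.5%. A null result could well be inconclusive.

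Part of this stands. The power figures are undocumented, and the D.3.3 example does contradict the sentence it illustrates. The rest does not carry. The tension with A.1 is an inference, not a statement in the text. Lack of research on ACE inhibitors and CSF Aβ leaves the 8% without a source, but it does not mean the team had no SD: Sections C.2 and C.3 describe their own 4-month treatment studies in at-risk adults, with CSF data on 46 completers. That is a possible source, though D.4 does not name it. No passage tells the reader to treat non-significance as evidence of no effect. D.4's list of data for transfer names CSF Aβ and ACE but neither FMD nor AAIx, so the document does not show that the FMD claim bears on the second site's analyses.

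**Conclusion.** No change to the plan is called for. The concern divides into three parts:

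- **Missing detail.** D.4 omits the SDs, the source of the 8% and the endothelial effect. The Aβ claim is conditional on an SD of percent change of about 6.0% (6.3% to 6.9% with baseline adjustment, at assumed correlations of 0.8 to 0.5). The document neither meets nor breaks that condition, so the figure is unverified, not wrong.
- **A clerical slip.** The D.3.3 illustration has the opposite sign to its sentence and the wrong comparator for this trial. It is rationale text that D.4 does not cite, and no analysis uses it.
- **A reading already closed off.** The treatment effect is the comparison with placebo in the aims and in D.4.

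The trial is complete and its results are published. Removing or rewriting the prospective sample-size rationale now would alter no sample size, test or estimate, and doing so after results are known has its own cost. An analyst would report the difference between arms with its confidence interval and judge the 8% against that interval, whatever D.4 says about power. This rests on the t-test approximations above and on assumed SDs and correlations. A documented SD of change well above 6% would show the 80% figure to be too high, but would still leave the planned analysis as it is.
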